8. OUTPUT PRESENTATIONS

[Appendix 1](#) shows conventions for presentation of data in outputs.

Document: \\weedc-vnasc01\BIOSdata\F2G\F901318\ [Redacted]
Author: [Redacted] Version Number: 3.0
Version Date: 06Apr2023
Template No.: CS_TP_BS016 Revision 6 Reference: CS_WI_BS005
Effective Date: 02Dec2019

F2G Ltd.
PROTOCOL F901318/0032

The templates provided with this SAP describe the presentations for this study and therefore the format and content of the summary tables, figures, and listings to be provided by [REDACTED] Biostatistics. Minor modifications may be made to tables, figures, and listings to accommodate the data.

9. DISPOSITION AND WITHDRAWALS

All patients who provide informed consent will be accounted for in this study.

9.1. DISPOSITION

The number of patients enrolled, completed or prematurely withdrawn from main study participation with the primary reason for premature main study withdrawal will be presented overall and by Baseline DRC-adjudicated disease category, as relevant, using absolute and relative frequencies (n and %).

Similarly, the number of patients enrolled, treated, completed or prematurely discontinued from main study treatment together with the primary reason for premature main study treatment discontinuation will be summarised.

The number of patients enrolled for each centre and country will be summarised (n and %).

The number of patients included in each analysis set will be summarised. The decision to exclude patients from any of the analysis sets will be finalised at a DR meeting with the Sponsor prior to final database lock. Such excluded patients will be listed and a summary of the main reason(s) for exclusion will be provided. Reason(s) for exclusion can be protocol deviations or other factors that may affect the efficacy outcome or treatment of the patient.

Inclusion/exclusion criteria exceptions, i.e. those patients who met exclusion criteria or who did not meet inclusion criteria but were included in the study and received treatment, will be listed.

All patients (including patient number and site number) whose trial participation was impacted by COVID-19 will be presented in a listing, describing the particular impact.

The number of patients entering the extended treatment phase after completing main study phase, and those not entering the extended treatment phase will be summarised.

The above summaries and listings will be presented for the ENR set.

Document: \\ieedc-vnasc01\BIOSdata\F2G\F901318 [REDACTED]
Author: [REDACTED] Version Number: 3.0
Version Date: 06Apr2023
Template No.: CS_TP_BS016 Revision 6 Reference: CS_WI_BS005
Effective Date: 02Dec2019

9.2. PROTOCOL DEVIATIONS

- Protocol deviations identified during the conduct of the study will be captured in the CTMS PD log.
- The CTMS PD log will be used as provided. No additional deviations are to be programmed on the statistical database to be reconciled with the CTMS PD log.
- Major/critical protocol deviations as collected during the conduct of the study and as authorised prior to final database lock will be summarised by type and severity; and a by patient listing with the specific details for all protocol deviations will be provided. The summaries and listings will be presented for the ITT set.
- All protocol deviations relating to COVID-19 will in addition be summarised by type and severity, and a by patient listing with the specific details will be provided.
- Severity of protocol Deviations:
 - Critical: Deviation from protocol related procedures that threaten integrity of data, adversely affect patients and/or could invalidate acceptability of a study (or part of it). Such deviations require immediate action.
 - Major: Deviation from protocol related procedures that could affect integrity of the data or adversely affect patients. Such deviation requires timely action.
 - Minor: Deviations from accepted procedures that will not adversely affect patient/data but should be dealt with appropriately.

10. DEMOGRAPHIC AND OTHER BASELINE CHARACTERISTICS

Demographic data and other baseline characteristics will be presented for the ITT and mITT populations.

No statistical testing will be carried out for demographic or other baseline characteristics.

Descriptive statistics and listings for the following demographic and other baseline characteristics will be reported for this study:

- Age (years) - calculated relative to date of informed consent
- Age (years) Categories

Document: \\weedc-vnasc01\BIOSdata\F2G\F901318\ [Redacted]
Author: [Redacted] Version Number: 3.0
Version Date: 06Apr2023
Template No.: CS_TP_BS016 Revision 6 Reference: CS_WI_BS005
Effective Date: 02Dec2019

F2G Ltd.
PROTOCOL F901318/0032

- <18 years
 - ≥ 18 - <65 years
 - ≥ 65 years
- Gender at birth
 - Race
 - Ethnicity
 - Patient's hospitalisation status at screening
 - Baseline Weight (kg)
 - Height (cm)
 - Body Mass Index (BMI) (kg/m²) [derived]
 - Investigator Baseline Assessment of Fungal Infection
 - IFD under study
 - Categorization of IFD (Probable/Proven), and Method for "Proven"
 - Shipped to Mycology or Cocci Serology Central Lab (Yes/No)
 - Reason for limited treatment options
 - a) Known or predicted resistance of the infecting isolate to all licensed agents,
 - b) Failure of available therapy,
 - c) Intolerance to available therapy,
 - d) Inability to manage DDIs and alternative licensed agents are either predicted to be ineffective or are contraindicated,
 - e) Inability to produce therapeutic drug levels and alternative licensed agents are either predicted to be ineffective or are contraindicated,
 - f) An intravenous (IV) only option (e.g. amphotericin) has produced a clinical response, and it is standard practice to switch to an oral azole to complete therapy, and at least one of the following is true:

Document: \\weedc-vnasc01\BIOSdata\F2G\F901318\ [Redacted]
Author: [Redacted] Version Number: 3.0
Version Date: 06Apr2023
Template No.: CS_TP_BS016 Revision 6 Reference: CS_WI_BS005
Effective Date: 02Dec2019

F2G Ltd.
PROTOCOL F901318/0032

- i. Azole-resistance is known based on susceptibility testing of the infecting isolate,
 - ii. Azole-resistance is predicted by polymerase chain reaction (PCR or similar molecular diagnostic tool),
 - iii. Azole-resistance is suspected based on epidemiological or clinical grounds,
 - iv. An azole would be acceptable therapy, but it is known or predicted that unmanageable DDIs will occur.
- g) Other received MM approval.
- Duration (days) from Baseline fungal infection start to first administration of study medication [derived]
 - Investigator Baseline Assessment of Additional Fungal Infection
 - Additional baseline fungal infection
 - 42 (days) from additional Baseline fungal infection start to first administration of study medication [derived]
 - Baseline DRC adjudicated disease category
 - Second Baseline DRC-Adjudicated Disease Category
 - Baseline objective measure of infection activity/ Initial Categorization of IFD (Presented in Separate Table)
 - Host factors
 - Clinical features (Radiology and Bronchoscopy)
 - Mycological criteria
 - Clinical signs, symptoms and physical findings of IFD
 - If a combination of the above objective measures is applicable subgroup will be “Combination of objective measures”. Details on objective measures may be found in the patient listing pertaining to Initial categorization of IFD.
 - Site
 - As collected on the Initial Categorization of Invasive Fungal Disease eCRF page, item named Site. If more than one site is applicable, subgroup will be “Multiple sites”. Details on these

Document: \\weedc-vnasc01\BIOSdata\F2G\F901318\ [Redacted]
Author: [Redacted] Version Number: 3.0
Version Date: 06Apr2023
Template No.: CS_TP_BS016 Revision 6 Reference: CS_WI_BS005
Effective Date: 02Dec2019

F2G Ltd.
PROTOCOL F901318/0032

multiple sites may be found in the patient listing pertaining to Initial categorization of invasive fungal disease.

- Screening Assessment of IFD
 - Radiology findings
 - Mycology findings
- Pre-Study Course for Fungal Infection Under Study (listed)
 - Was qualifying fungal infection a breakthrough infection (fungal infection that occurred while receiving a mould-active antifungal agent)
 - Was specific therapy begun in response to diagnosis of qualifying fungal infection
 - Duration for each antifungal used as specific therapy for qualifying fungal infection and timing relative to start of study drug.
 - Nature of response to prior antifungal therapy at time of enrolment
 - Was surgery carried out as therapeutic modality for this IFD

10.1. DERIVATIONS

- $BMI (kg/m^2) = weight (kg) / [height (m)]^2$
- $Age (years) = floor of ([date of informed consent - date of birth] / 365.25)$
- If the date of birth is partial, then the date of birth will be imputed as follows for the calculation of age:
 - If only the day is missing, then the 15th day of the month will be used as the day.
 - If the day and month are missing, then the 02 Jul will be used as the day and month (i.e. the 183rd day of the year).
- $Duration (months) from event to first administration of study medication = floor of ([date of first administration of study medication - date of event] / 30.4375)$

Document: \\weedc-vnasc01\BIOSdata\F2G\F901318\ [redacted]
Author: [redacted] Version Number: 3.0
Version Date: 06Apr2023
Template No.: CS_TP_BS016 Revision 6 Reference: CS_WI_BS005
Effective Date: 02Dec2019

F2G Ltd.
PROTOCOL F901318/0032

11. PRIMARY UNDERLYING DISEASE OR CONDITION, INFECTIOUS DISEASE HISTORY AND MEDICAL HISTORY

Primary Underlying Disease or Condition, Infectious Disease History and Medical History descriptive statistics based on the ITT analysis set will be presented.

- Primary Underlying Disease or Condition data will be coded using the most recent version of Medical Dictionary for Regulatory Activities (MedDRA).
 - Data captured on the Primary Underlying Disease or Condition page of the eCRF will be presented by System Organ Class (SOC) and Preferred Term (PT).
 - Primary Underlying Disease or Condition data captured are any underlying disease or condition that predisposes a patient to IFD.
 - If more than one primary underlying disease or condition is applicable, subgroup will be “Multiple primary underlying diseases or conditions”. Details on these multiple primary underlying diseases or conditions may be found in the patient listing pertaining to Primary underlying disease or condition
 - Other variables to be summarised include:
 - Duration (months) from initial diagnosis to first administration of study medication [derived]
 - Malignancy (Remission or Relapse)
 - Duration (months) from remission to first administration of study medication [derived]
 - Duration (months) from relapse to first administration of study medication [derived]
 - Solid organ transplant (Yes/No)
 - Type of organ transplanted
 - Duration (months) from solid organ transplant to first administration of study medication [derived]
 - Bone marrow or other progenitor cell transplant (Yes/No)
 - Type of bone marrow or other progenitor cell transplant
 - Type of cells

Document: \\weedc-vnasc01\BIOSdata\F2G\F901318\ [Redacted]
Author: [Redacted] Version Number: 3.0
Version Date: 06Apr2023
Template No.: CS_TP_BS016 Revision 6 Reference: CS_WI_BS005
Effective Date: 02Dec2019

F2G Ltd.
PROTOCOL F901318/0032

- Duration (months) from bone marrow or other progenitor cell transplant to first administration of study medication [derived]
 - Current or recent (within the past 3 months) history of graft versus host disease (GVHD)
 - Duration (months) from start of GVHD to first administration of study medication [derived]
 - Grade of GVHD
- Infectious Disease History will be coded using the most recent version of MedDRA.
 - Data captured on the Infectious Disease History page of the eCRF will be presented by SOC and PT.
 - Infectious Disease History captured are any invasive fungal disease (other than the IFD under study) or any other fungal or viral infection within the 6 months prior to first administration of study medication, or any bacterial infections within 1 month prior to first administration of study medication.
 - Medical History will be coded using the most recent version of MedDRA.
 - Medical History conditions captured are any existing clinically significant baseline conditions and/or clinically relevant medical conditions (other than the disease under study) occurring within the 3 months prior to first study medication administration, or any other major medical history occurring at any prior time (no time restriction) with the potential to affect immune status.
 - Data captured on the Medical History page of the eCRF will be presented by SOC and PT.
 - Active disease status at baseline based upon medical review (categories of Improving on prior therapy, Active-Stable, Active-Slowly progressing, Active-Rapidly progressing, Active-Little Prior therapy)

11.1. DERIVATIONS

- Duration (months) from event to first administration of study medication = floor of $([\text{date of first administration of study medication} - \text{date of event}] / 30.4375)$

12. MEDICATIONS

Concomitant and prior Antifungal Medications will be coded using the most recent version of World Health Organisation Drug Dictionary (WHO-DD) and descriptive statistics by ATC level 4 for all concomitant medications

Document: \\weedc-vnasc01\BIOSdata\F2G\F901318\ [Redacted]
Author: [Redacted] Version Number: 3.0
Version Date: 06Apr2023
Template No.: CS_TP_BS016 Revision 6 Reference: CS_WI_BS005
Effective Date: 02Dec2019

and antifungal concomitant medications based on the ITT analysis set will be presented.

See [appendix 2](#) for handling of partial dates for medications, in the case where it is not possible to define a medication as prior, concomitant or post the medication will be classified by the worst case; i.e. concomitant. A medication may be classed as both 'prior' and 'concomitant'.

- 'Prior' medications are medications which were started prior to the first dose of study medication.
- 'Concomitant' medications are medications which were:

started prior to, on or after the first dose of study medication but prior to last dose of study medication,

AND ended on or after the date of first dose of study medication or were ongoing at the end of the study.

- 'Post' medications are medications started after the last dose of study medication (to be listed only).
- Therapeutic drug monitoring data on medications resulting in dose adjustments will be listed.
- Concomitant antifungal usage (Yes/No)
 - number of days of concomitant antifungal usage on study
- Summary will be presented by systemic antifungal medication and non-antifungal medications. Systemic antifungals will be confirmed and provided by medical review process.
- Plot for duration of antifungal medications will also be presented.

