The specific combination of fluconazole (CYP3A4 and CYP2C9 inhibitor) and F901318 has been studied in man and exposure to fluconazole has been shown to increase mean AUC₀₋₁₂ and C_{max} of F901318 by 2.0 and 1.7-fold, respectively. *In vitro* and *in vivo* studies have shown that F901318 is a weak inhibitor of CYP3A4; in a clinical study treatment with F901318 resulted in an approximately 1.6-fold elevation of midazolam exposure. F901318 also shows potential for inhibition of the P-gp, BCRP, and BSEP transporters in *in vitro* studies, and whilst the potential for drug interactions is thought to be low, careful monitoring may be needed for sensitive substrates of these transporters which have narrow therapeutic windows.

Based on these findings, caution should be exercised when F901318 is dosed together with any CYP inducer (this may reduce F901318 levels) or inhibitor (this may increase F901318 levels). In addition, F901318 could increase the exposures of compounds metabolized by CYP3A4.

The Investigator is advised to consult with the MM on concomitant medications that either are metabolized by the liver or that influence hepatic metabolism. Concomitant administration of inhibitors of human DHODH (teriflunomide and leflunomide) is prohibited. Co-dosing with moderate or strong CYP3A4 or 2C9 inhibitors will require a dose reduction for F901318 and guidance on dose adjustment must be sought from the MM. It is anticipated that co-dosing with strong CYP inducers (e.g., phenytoin and rifampicin) will significantly reduce F901318 exposures and is discouraged. It is anticipated that co-dosing with immunosuppressive agents

that are sensitive CYP3A4 substrates (e.g., cyclosporine, sirolimus, or tacrolimus) will be possible, [REDACTED].

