3.3 Exploratory Objectives

- Evaluate dose adaptation and drug-drug interaction (DDI) management strategies.
- Assess potential drug interactions associated with F901318 treatment.

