5.9.1.5 Co-Dosing F901318 with Sensitive and Moderately Sensitive CYP3A4 Substrates

Monitoring of circulating levels of the concomitant medication is required when co-dosing F901318 with sensitive and moderately sensitive CYP3A4 substrates.

F901318 is a perpetrator of potential DDIs with CYP3A4 substrates. As F901318 is a weak inhibitor of CYP3A4, co-dosing with sensitive and moderately sensitive CYP3A4 substrates may increase exposure of these substrates. Consultation with the MM and use of TDM for the substrate are advised if the combination cannot be avoided.

For those concomitant medications which are sensitive and moderately sensitive CYP3A4 substrates and which undergo routine TDM (such as transplant drugs), changes in concomitant drug treatment and all TDM results for the concomitant medication will be recorded. If the patient is receiving the concomitant medication prior to receiving F901318, a baseline TDM sample should be sent for analysis prior to F901318 treatment commencing. Further TDM sampling should be performed on a schedule based on the Investigator's judgment regarding the given medication.

Sensitive substrates: alfentanil, avanafil, budesonide, buspirone, conivaptan, cyclosporin, darifenacin, darunavir, dasatinib, dronedarone, ebastine, eletriptan, eplerenone, everolimus, felodipine, ibrutinib, indinavir, lomitapide, lovastatin, lurasidone, maraviroc, midazolam,

naloxegol, nisoldipine, quetiapine, ruxolitinib, saquinavir, sildenafil, simvastatin, sirolimus, tacrolimus, ticagrelor, tipranavir, tolvaptan, triazolam, and vardenafil.

Moderately sensitive substrates: alprazolam, aprepitant, atorvastatin, colchicine, eliglustat, pimozone, rilpivirine, rivaroxaban, tadalafil.

See also further guidance on sensitive and moderately sensitive CYP3A4 substrates at the FDA website.

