8.2.4 Safety Endpoints

Descriptive statistics will be used to present the safety outcomes including:

- Changes in concurrent medication dose and/or frequency resulting from potential DDIs
- Hospitalisations
- Overall exposure, individual dose modification, dose intensity.
- Incidence of treatment-emergent and other (including but not limited to):
 - AEs
 - SAEs (including deaths)
 - AEs leading to death
 - Liver-related AEs
 - AEs leading to premature treatment discontinuation
 - AEs leading to premature study withdrawal
 - AEs by relationship

- AEs by severity (CTCAE grade)
- AESIs
- Change from baseline in clinical laboratory test results and incidence of pre-defined treatment-emergent abnormalities (CTCAE)
- Liver-related toxicity: Incidence and time-to-event analyses of elevations in ALT, AST, bilirubin, as described in detail in Section 6.4.2.3.
- Change from baseline in ECG results and incidence of pre-defined treatment-emergent abnormalities (CTCAE)
- Change from baseline in vital signs (including weight and BMI) and incidence of pre-defined treatment-emergent abnormalities (CTCAE)
- [REDACTED]
- Physical examination: Any abnormal clinically significant findings, as judged by the Investigator, will be listed in a by-patient data listing only.

A treatment-emergent AE (TEAE) is defined as any AE starting or worsening on or after the first dose of study drug up to and including last dose of study drug or during the post-treatment FU. Treatment-emergent AEs which occur in the main study phase or FU will be presented in the study report; TEAEs which occur in the ET phase or post-ET FU will be presented in the report addendum.

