2.3. EXPLORATORY OBJECTIVES

The exploratory objectives are:

- To evaluate dose adaptation and drug-drug interaction (DDI) management strategies.
- To assess potential drug interactions associated with F901318 treatment.

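### Co-medication dose changes due to drug interactions are a protocol safety outcome promised descriptive statistics, but the SAP plans only a listing selected on dose adjustment, with no denominator

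*SAP*

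**What the plan says.** **The outcome.** Protocol 8.2.4 opens with "Descriptive statistics will be used to present the safety outcomes including", and the first item under it is "Changes in concurrent medication dose and/or frequency resulting from potential DDIs". The synopsis names the same item among the safety criteria. Modification of the F901318 dose is a separate item in both lists.

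**The mechanism.** The clinical pharmacology background (Protocol 2.1.3) describes F901318 as a weak CYP3A4 inhibitor and reports that treatment "resulted in an approximately 1.6-fold elevation of midazolam exposure".

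**The data.** For sensitive and moderately sensitive CYP3A4 substrates under routine therapeutic drug monitoring (TDM), such as transplant drugs, Protocol 5.9.1.5 says that treatment changes and "all TDM results for the concomitant medication will be recorded". A patient already on the drug should have a baseline level taken before F901318 starts. Later sampling follows the Investigator's judgment.

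**The objective.** SAP 2.3 keeps the protocol's exploratory aim: "To assess potential drug interactions associated with F901318 treatment".

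**The SAP output.** Section 12 says: "Therapeutic drug monitoring data on medications resulting in dose adjustments will be listed". It otherwise summarises medication use by ATC level 4. Section 17.1.1 summarises olorofim trough and intensive PK parameters by group of CYP2C9/CYP3A4 inhibitors and CYP3A4 inducers.

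**The concern.** The protocol commits to a descriptive result for this outcome, and the SAP turns it into a listing of cases in which a dose was adjusted. A listing chosen because the event happened shows the events but not the patients at risk of them. It cannot answer the question behind the outcome: of the patients taking a drug whose level F901318 may raise, how many needed its dose or frequency changed?

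F901318's effect on other drugs is a foreseen interaction for which the protocol sets up monitoring and data capture. The sensitive substrates named in Protocol 5.9.1.5 include cyclosporin, sirolimus and tacrolimus, and solid organ and stem cell transplant are among the underlying conditions by which efficacy may be summarised. A reader of the study report would expect at least a count and a percentage. If the listing-only approach was deliberate, SAP 3.3 is where it should be declared.

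**Working it through.** No figure in the plan bears on this, so there is nothing to reproduce. The check traces the outcome from promise to output.

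1. **Promise.** Protocol 8.2.4: descriptive statistics for co-medication dose or frequency changes due to potential interactions. A descriptive result for a yes/no event is n/N (%), where N is the number of patients taking a relevant substrate and n the number of those with such a change.

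2. **Data for n and N.** Protocol 5.9 has all concomitant medication, and changes to it, recorded. Protocol 5.9.1.5 names the relevant substrates. Both counts can come from data that the protocol already has recorded.

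3. **Where the SAP might produce n/N.**
   - *Section 12, TDM listing.* It is restricted to cases with a dose adjustment and does not say whether the adjusted drug is the substrate or F901318. At best it shows the patients who make up n, and only where levels were measured. It gives no N.
   - *Section 12, medication tables.* These give use by ATC level 4. SAP 3.3 states that preferred terms are not presented. The tables carry no dose changes, and N for a named substrate cannot be read from them.
   - *Section 18.1.8, adverse events leading to dose adjustment.* These are identified from the action taken with study treatment, so they concern the F901318 dose. Protocol 8.2.4 treats that as a different item.
   - *Section 17.1.1.* The outcome there is olorofim exposure and the co-medication is the grouping factor, which is the reverse direction.

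   None of these yields n/N.

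4. **Declaration.** SAP 3.3 does declare other departures, including the switch to ATC level 4 and the removal of the tables of AST/ALT elevation with symptoms. Its legible items do not mention this outcome. One item is largely redacted, but it cites Protocol 8.9.4.3, whereas this outcome sits in 8.2.4.

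5. **Size.** The documents do not state how many patients take a sensitive or moderately sensitive substrate. Neither N nor the precision of n/N can be computed, and none is claimed.

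**The case against.** The strongest reply is that little is lost, and several parts of it stand.

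- **The exploratory objective is served.** A reader might infer that the interaction objective gets no result. The documents do not support that. The objective names no direction, and SAP 17.1.1 gives a real, if one-sided, result, with means and 95% confidence intervals in figures for the intensive PK day.
- **Unadjusted levels may still be listed.** A reader might infer that levels without a dose change will not be shown at all. That is not established. SAP 6 has a general rule that relevant raw and derived variables are listed by patient, SAP 20 does not name TDM among the data left out, and SAP 8 refers to output templates that are not available here.
- **Clinical harm is captured elsewhere.** Protocol 6.4.1 counts the clinical consequences of a suspected interaction as adverse events, so they enter the SAP 18.1 tables. Creatinine is graded and summarised under SAP 18.2.
- **A before/after level ratio would not isolate F901318.** Sampling times follow the Investigator's judgment (Protocol 5.9.1.5), and the baseline may be up to 7 days old (Table 1 footnotes). Protocol 5.9.2.1 has patients on isavuconazole or posaconazole switched to fluconazole, so other interacting drugs change around entry. Omitting such a ratio is defensible in a single-arm descriptive study.
- **Redaction.** Parts of SAP 3.3 and all of 18.2.4, 18.7 and 19 are wholly or largely blacked out. Coverage there is unlikely but cannot be ruled out.

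None of this supplies the promised descriptive result. Listing more levels adds no denominator, and adverse event tables do not count dose changes made to prevent an event.

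**Conclusion.** The point holds in a narrow form. One safety outcome that Protocol 8.2.4 says will be described statistically has no summary in the legible SAP. Its only specific output is a listing selected on the outcome, and no legible item of SAP 3.3 declares the departure.

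The documents do not support the wider inferences that the exploratory objective goes unanswered, that levels without a dose change are suppressed, or that the trial could have estimated how much F901318 raises substrate levels. The 1.6-fold figure is for midazolam in a clinical study. It explains why the outcome was named, but it does not size the effect on other substrates here.

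The primary analysis is unaffected. The conclusion rests on the legible text and on the redacted SAP sections not holding the missing table. It is worth correcting because the protocol made the commitment and the repair is small.

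**What to change.** In SAP 12:

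1. **Add one descriptive table.** Population: patients in the safety analysis set who receive a sensitive or moderately sensitive CYP3A4 substrate, as named in Protocol 5.9.1.5, during the main phase. Show n/N (%) with a substrate dose or frequency change recorded as due to a potential interaction. Present it overall and for each substrate with at least 3 patients, the threshold already used in SAP 17.1.1. Count attributed changes only, to match the outcome's wording; counting every change after F901318 starts would include routine titration. If attribution is not a field on the eCRF, state how it will be assigned before database lock.
2. **List all substrate TDM results**, whether or not a dose changed, and say so explicitly in place of the present sentence.
3. **Treat any level summary as optional.** A ratio of dose-normalised on-treatment level to baseline may be added if labelled exploratory, with a note that it cannot be read as the size of F901318's effect.

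If the sponsor prefers listing only, SAP 3.3 should declare and justify it; the outcome would then still lack the promised summary.

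The cost is one small table and a wider listing, from data the protocol already has recorded. Some substrates will have few patients, so their percentages will be imprecise. Nothing here bears on how any drug is dosed or monitored.
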